APPENDIX 5 (ARM A) Decitabine and Rapamycin

												D	ays											
Tests	Pre	1	2	3	4	5	6	7	8	9	10	11	12	13	14	15	16	17	18	19	20- 22	22-26	28	EOS
Decitabine		X	X	X	X	X	X ¹⁰	X ¹⁰	X ¹⁰	X10	X ¹⁰													
Rapamycin							X11	X11	X11	X11	X ¹¹	X	X	X	X	X	X	X	X	X	X			
History & Physical	X	x																						
CBC w/diff & plts	X	X						X^3																
Chemistries	X	X8						X^3																
LDH	X					X		X^3																
Urate	x	x						X ⁴																
Bone marrow	X										X1												X1	X1
Flow Cytometry	X																					X		
Cytogenetic Studies	X																					X		
DIC Panel	x																							
Molecular Studies ¹⁴	X																							
Bone marrow for Correlative Studies	X ⁵ 40cc										X540cc											X540cc		
Blood for correlative studies	X ⁷ 10cc										X ⁷ 10cc											X ⁷ 10cc		
EKG/CXR	X																							
U/A, PT, PTT, Pregnancy	X																							
Chimerism	X^2																						X^2	
Rapamycin Levels		X12													X9						X ⁹			
Evaluation of Response																							X ⁶	X ⁶
Long Term Follow Up																								X ¹³

- 1. Aspirate only in cycle 1 on day 10-11 and biopsy and aspirate at days 22-26 of cycles 1 and 3 for disease assessment, and at end of study. Marrows may also be performed when clinically indicated at other times for disease assessment. Substitute peripheral blood if aspirate/marrow cannot be obtained.
- In those patients who have had an allogeneic transplant by chromosome (sex mismatched transplants) or by PCR assay. This can be done on either blood or marrow at physicians' choice.
- 3. Twice per week or as clinically indicated
- 4. As indicated clinically
- 5. 40 cc aspirate in green top (heparinized) tubes; if marrow is a dry tap, substitute 40 cc blood total
- 6. Cycles 1 and 3 only and at end of study or study discontinuation.

- 7. 10cc in green top tube.
- 8. Include cholesterol and triglycerides on day 1 of each cycle only.
- Rapamycin levels will be drawn (trough) on days 14 and 21. Patients will be asked to hold the daily dose until the level is drawn.
- 10. Decitabine is given on days 1-10 during cycle 1. In subsequent cycles, decitabine is given days 1-5.
- 11. Rapamycin starts on Day 6 starting with Cycle 2
- 12. Cycle 2 Day 1 only
- 13. Every 6 months for up to 2 years after date of last treatment
- 14. Molecular studies completed previously are acceptable if results are in the medical record.

Version date: 09Aug2017

All time points refer to all cycles except where noted. The window for protocol visits and assessments is +/- 3 days.

Correlative studies are described in Section 8 above. Blood and marrow for correlative studies will be sent to the BMT laboratory ([name]). The study coordinator will contact, [name] or her laboratory technician for pick up. All are available through the paging system ([name] or web paging).

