4.1.1 Study schema

Note: Those patients with morphologic M4/M5 subtypes²⁸ will be treated on Arm B and all other subtypes on Arm A. At study entry, all patients will have samples procured for testing of eIF4E expression but this will not determine allocation to arm A or B which will be made solely on the basis of FAB subtype. M4 subtype is acute myelomonocytic leukemia and M5 acute monocytic leukemia.

- Decitabine (Arms A and B)
- 20mg/m2 will be given as an intravenous infusion daily for 10 consecutive days starting on day 1 of cycle 1.
- In subsequent cycles, decitabine will be given for 5 days (day 1-5)

Rapamycin (Arm A)

- o For non-M4/M5 AML cases²⁸
- A 6 mg loading dose will be administered on Day 11 in cycle 1 and day 6 in subsequent cycles. Thereafter, 2 mg/day will be administered per schedule below. This may be reduced to 1 mg/day if levels are elevated (>15 ng/mL).
- o Toxicities will be as defined in section 9 using NCI Common Toxicity Criteria for Adverse Events (CTCAE (version 4.0) Appendix 3)
- o Rapamycin will be given from day 11 to 22 in cycle 1 and on days 6 to 22 in subsequent cycles.

Dose Level	Rapamycin	Decitabine
Level -1	1 mg	20 mg/m2
Level 1	2 mg	20 mg/m2

The rapamycin dose for phase II of the study was chosen based on results from the phase I study (ULEU08049).

Ribavirin (Arm B)

For M4/M5 cases²⁸—These patient are anticipated to have high eIF4E expression as expressed by Western blotting²⁴.

In cycle 1, ribavirin will be dosed from Day 11 through Day 28.

In subsequent cycles, ribavirin will be started on Day 1 on a continuous basis until study completion. These doses were chosen based on those found effective and tolerated in previous studies²⁴.

Dose level cohorts are listed in the table below. Subject enrollment will start at **Dose Level 1** (1000 mg). Enrollment in subsequent dose levels (escalation to Dose level 2 and 3, or de-escalation to Level -1 and -2) will follow the dose escalation and dose de-escalation plans as outlined below.

ULEU-13049 14 Version date: 09Aug2017

Dose Level	Ribavirin	Decitabine	Description
Level -2	600 mg bid	20mg/m2	Dose de-escalation cohort
Level -1	800 mg bid	20mg/m2	Dose de-escalation cohort
Level 1	1000 mg bid	20mg/m2	Initial cohort
Level 2	1200 mg bid	20 mg/m2	Dose escalation cohort
Level 3	1400 mg bid	20mg/m2	Dose escalation cohort

Dose Escalation Plans for Ribavirin (Arm B)

Number of patients with DLT at a given dose level	Escalation Decision Rule

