0 out of 3	Enter 3 patients at the next dose level
≥ 2	Dose escalation will be stopped. This dose level will be declared the maximally administered dose (highest dose administered). Three (3) additional patients will be entered at the next lowest level if only 3 patients were treated previously at that dose.
1 out of 3	Enter at least 3 more patients at this dose level. – If 0 of these 3 patients experience DLT, proceed to the next dose level. -If 1 or more of this group suffer DLT, then dose escalation is stopped, and this dose is declared the maximally administered dose. Three (3) additional patients will be entered at the next lowest dose level if only 3 patients were treated previously at that dose.
≤ 1 out of 6 at highest dose level below the maximally administered dose	This is generally the recommended phase 2 dose. 6 patients must be entered at the recommended phase 2 dose before going to Phase 2.

An ad hoc confidential person will ensure that no unexpected adverse events have occurred at each dose level before enrollment on the next dose level commences. This will be handled through the DSMB of the James P Wilmot Cancer Center. THIS WILL REQUIRE THAT THE LAST PERSON ENROLLED AT THE PRIOR COHORT HAS BEEN FOLLOWED FOR 30 DAYS FROM THE START OF THERAPY.

Dose De-escalation: If 1000 mg bid proves to be the MTD, a cohort at 800 mg bid will be treated, and if that is too toxic, one at 600 mg bid will be enrolled (level -2). No further dose de-escalation would be planned. Safety assessment at each cohort would be as indicated above.

4.1.1.1

Cycle Duration

Cycles will begin on an every 28 day basis which may be extended to 30 days to account for weekends, holidays, logistics of marrow aspirate and biopsy scheduling.

Routine Clinical Monitoring.

Routine CBC with differential and platelets as well as a comprehensive metabolic profile including renal and hepatic function will be evaluated on a twice weekly basis and more frequently as cytopenias or metabolic abnormalities indicate. For those patients receiving rapamycin, a trough Rapamycin level will be performed at day 14 and 21 of each cycle.

Marrow Status Monitoring.

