4.5.1.2 Dose modifications for hematologic toxicity

Grade 2

No dose interruptions will be performed for grade 1 or 2 hematologic toxicity because it is anticipated that all patients may become pancyopenic as a result of treatment or from the AML itself.

Grade 3 or 4

No dose reductions will be performed for grade 3 or 4 anemia, neutropenia and thrombocytopenia. Patients will receive supportive care as specified in section 4.2. Cycles may be delayed up to a week in the event of stable disease if severe neutropenia and/or active infection are present until the infection is controlled and neutropenia stabilized or improving.

Dose modifications for other reasons

If vomiting occurs following rapamycin administration, an extra dose will not be given that day and antiemetics will be prescribed to enable resumption of the next day's dose.

Grade 3 infections, fatigue, weight loss, and electrolyte imbalances are anticipated in relapsed AML patients and will be appropriately treated but are not deemed study related toxicities and will not result in dose modifications.

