5.2 Rapamycin (from Rapamycin package insert)

Rapamycin can be obtained as Rapamune® from Wyeth-Ayerst Laboratories. It is approved for graft rejection prevention in kidney transplantation. It will be purchased from commercial sources for this protocol.

The oral solution must be protected from light and stored under refrigeration, 2 degrees Celsius to 8 degrees Celsius and it is stable for 24 months under these conditions. A slight haze may develop in refrigerated solutions, but the quality of the product is not affected. After opening, the solution should be used in 1 month. If necessary, it may be stored at temperatures up to 25 degrees Celsius for several days after opening (not longer than 30 days). Product may be stored in an amber syringe for a maximum of 24 hours (at room temperature or refrigerated). Discard syringe after use. Solution should be used immediately following dilution. The tablet should be stored at room temperature (20 degrees Celsius to 25 degrees Celsius) and protected from light.

Absorption: Rapid

Volume of distribution: 12L/Kg (+/- 7.52L/kg) Protein binding: 92%, primarily to albumin

Metabolism: Extensively hepatic via CYP3A3/4 and P-glycoprotien

Bioavailability: 14%

Half-life elimination: Mean: 62 hours

Time to peak: 1 - 3 hours

Excretion: Feces (91%); Urine (2.2%)

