5.2.1. Adverse reactions

5.2.1.1. Systemic >10%:

Central nervous system: Insomnia, nervousness

Gastrointestinal: Increased appetite, indigestion, esophagitis

Dermatologic: Hirsutism

Endocrine/metabolic: Diabetes mellitus Neuromuscular & Skeletal: Arthralgia

Ocular: Cataracts Respiratory: Epistaxis

Metabolic: Increased triglycerides or cholesterol

<1% of case reports:

Seizures, mood swings, headache, delirium, hallucinations, euphoria, skin atrophy, bruising, hyperpigmentation, acne, amenorrhea, sodium and water retention, Cushing's syndrome, hyperglycemia, bone growth suppression, abdominal distention, ulcerative esophagitis, pancreatitis, muscle wasting, hypersensitivity reactions, pneumonitis in renal transplant patients, microangiopathic anemia in GVHD prophylaxis regimens only.

ULEU-13049 24 Version date: 09Aug2017

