6.0 STUDY CALENDAR (Appendix 5)

Baseline evaluations are to be conducted within 1 week prior to the start of the protocol unless otherwise specified.

Before beginning the treatment protocol, each patient will have the following performed:

- Complete history and physical exam including: Demographics, past medical and surgical history, medications, allergies, vital signs, height, weight, systemic exam including neurological exam
- EKG and Chest x-ray
- Bone marrow aspirate/biopsy, cytogenetics, molecular diagnostic studies to assess for the
 presence of FLT-3 or NPM-1 mutations and flow cytometry within 2 weeks of treatment.
 If these studies were performed elsewhere, an aspirate only will be performed to obtain
 material to perform the baseline correlative studies that are part of the protocol. (See
 section 8).
- CBC with differential, platelet count
- Chemistry including complete liver function tests, BUN/Cr, LDH and other electrolytes
- Uric acid level
- Urine analysis and urine pregnancy test for female patients of childbearing potential
- DIC panel
- Peripheral blood for correlative studies (See section 8 and Appendix 5)

After the beginning of each cycle, each patient will have the following tests performed at the noted time points:

- CBC with differential and platelets twice per week
- Chemistry including liver function tests, BUN/Cr and other electrolytes twice weekly
- Triglycerides and cholesterol on Day 1 of each cycle for those on Arm A (rapamycin) only
- Abbreviated physical examination and assessment of performance status
- A bone marrow aspirate only will be performed on Day 10 or 11 of therapy after completion of the decitabine and before initiation of rapamycin or ribavirin in CYCLE 1 ONLY for correlative studies including the phosphorylation status of mTOR effectors and stem cell frequency.
- A trough rapamycin level (arm A only) will be drawn on day 14 and 21 of each cycle. A level will also be drawn on Day 1 of Cycle 2 to assure a subtherapeutic level when decitabine is started in subsequent cycles only if the level on Day 21 was elevated.
- A bone marrow aspirate and biopsy will be performed after the completion of cylces 1, 3, and at the end of the study. This may occur on Days 22 through 26 of the cycle.
- A marrow aspirate and biopsy will also be performed at time of suspected disease progression and at study completion or at any other time the treating physician deems important for disease status determination

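### Every scheduled Arm A lipid draw falls on a day without rapamycin dosing and none follows the last cycle, so raised lipids may be under-ascertained (minor)

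*Combined protocol and SAP*

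**What the plan says.** Two places set the lipid schedule, and they agree. Section 6.0 lists "Triglycerides and cholesterol on Day 1 of each cycle for those on Arm A (rapamycin) only"; there the last word limits the test to Arm A. Footnote 8 to the Arm A calendar in Appendix 5 reads "Include cholesterol and triglycerides on day 1 of each cycle only"; there the same word limits the timing.

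The other scheduled chemistries do not fill the gap. Section 6.0 describes them as "Chemistry including liver function tests, BUN/Cr and other electrolytes twice weekly", and section 4.1.1.1 names renal and hepatic function. Neither mentions lipids, and the Arm A calendar marks no chemistries at end of study.

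On dosing, section 4.1.1 states "Rapamycin will be given from day 11 to 22 in cycle 1 and on days 6 to 22 in subsequent cycles". On timing, section 4.1.1.1 says "Cycles will begin on an every 28 day basis which may be extended to 30 days", section 4.5.1.2 adds "Cycles may be delayed up to a week in the event of stable disease", and the note closing the Arm A calendar allows visits and assessments to move by 3 days either way.

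Section 5.2.1, under its >10% heading, includes "Metabolic: Increased triglycerides or cholesterol". Section 5.2 gives "Half-life elimination: Mean: 62 hours".

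**The concern.** Lipids are tested in Arm A alone, so the test is evidently there to detect an effect of rapamycin. Yet day 1 is never a rapamycin dosing day. The protocol itself treats it as a point of low exposure: section 6.0 calls for a rapamycin level on day 1 of cycle 2, where the day 21 level was high, to confirm that the level has become subtherapeutic.

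At stake is how completely one expected laboratory toxicity is captured. Objective 1.2 in section 1.0 names safety of decitabine with rapamycin, and section 9.5 sends adverse event rates and toxicities by arm to the monitoring committees. A lipid rise usually causes no symptoms, so it tends to be recorded only if a scheduled test finds it. A rise that appears during dosing and fades before the next day 1 would go unrecorded, as would any rise in a patient's last cycle.

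**Working it through.** The plan states no lipid rate, so there is no figure to reproduce. The check is calendar arithmetic plus a decay calculation.

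**Inputs.** Lipid draws on day 1 (6.0; Appendix 5 Arm A, footnote 8). Rapamycin on days 11–22 in cycle 1 and 6–22 later (4.1.1). Cycle length 28 days, extendable to 30, with a delay of up to 7 days allowed in stable disease (4.1.1.1; 4.5.1.2). Window ±3 days (Appendix 5). Half-life 62 hours (5.2). Maximum six cycles (4.1.1.1).

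**Step 1: dosing days with a scheduled lipid draw.** Cycle 1 has 22 − 11 + 1 = 12 dosing days; each later cycle has 22 − 6 + 1 = 17. Over six cycles that is 12 + 5 × 17 = 97. A day 1 draw moved by +3 days falls on day 4, still before day 6 (or day 11 in cycle 1). Scheduled draws on dosing days: 0 of 97.

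**Step 2: gap from last dose to next draw.** Gap in days = (cycle length + 1) − 22 + window shift. Residual fraction = 0.5^(24 × gap / 62), assuming first-order decline at the mean half-life.

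| Cycle length | Window shift | Gap (days) | Residual drug |
|---|---|---|---|
| 28 | 0 | 29 − 22 = 7 | 0.5^(168/62) = 15% |
| 28 | −3 | 4 | 0.5^(96/62) = 34% |
| 30 | 0 | 9 | 0.5^(216/62) = 9% |
| 30 | −3 | 6 | 0.5^(144/62) = 20% |
| 35 (one-week delay) | 0 | 14 | 0.5^(336/62) = 2% |

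The cycle 1 draw is 11 − 1 = 10 days before the first dose.

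**Step 3: draws per patient.** A patient treated for *k* cycles has *k* scheduled draws, of which *k* − 1 follow any rapamycin. For *k* = 1 that is none; for *k* = 6 it is five. The rapamycin of the last cycle is never followed by a scheduled draw.

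**Step 4: is stopping after one cycle plausible?** Section 4.1.1.1 continues patients past cycle 1 only without overt progression. In the earlier phase I study of this combination (2.6), 5 of 13 patients had progressed by the end of cycle 1. The outcome counts given there add to 5 + 5 + 4 = 14, and progression may have been defined differently, so this is only a rough guide.

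**What cannot be computed.** The documents do not say how long lipids stay raised after rapamycin stops. If elevations persist fully until the next day 1, only those in the last cycle are missed. If they follow the drug level, most could be missed.

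**The case against.** The strongest reply is that this is the timing of one routine laboratory test and that the harm is not demonstrated. Much of that stands.

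- **No lipid endpoint exists.** The Arm A decision rests on response (Statistical Considerations). Lipid events enter only through general adverse event recording. A reader might infer that an Arm A lipid toxicity rate is being estimated wholly off drug; the plan defines no such rate.
- **Unscheduled tests are allowed.** Footnote 3 of the calendar permits chemistries when clinically needed, so the gap concerns scheduled draws only.
- **Off drug is too strong.** It is true of dosing days but not of exposure: 15% to 34% of the drug may remain 7 to 4 days after the last dose. A 7-day minimum gap is nominal, because the window permits 4.
- **The hold rule is not disabled.** A reader might infer that the rule in 4.5.1.1 for grade 2 or higher toxicity can never respond to lipids. It can: an unscheduled test may detect a rise during dosing, and a raised day 1 value in cycle 2 or later is known about 5 days before rapamycin restarts on day 6.
- **The >10% class comes from the package insert** of a drug approved in kidney transplantation. The documents do not show that it carries over to courses of 12 to 17 days at this dose.

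These points limit what can be claimed. They do not supply an on-treatment measurement, nor any value after the last cycle.

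**Conclusion.** The concern holds as a minor gap in safety ascertainment. By schedule, no lipid value is taken on any of up to 97 rapamycin dosing days, none is taken after the final cycle, and a patient who stops after cycle 1 contributes only a pre-rapamycin value. The calendar result rests on the written schedule and holds throughout the ±3-day window. The residual drug figures also assume first-order decline at the 62-hour mean half-life.

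Lipid elevations may be under-ascertained in Arm A; the documents do not allow the size to be estimated. They do not support saying that elevations are definitely under-reported, or that the hold rule cannot operate. The response-based decision for Arm A is unaffected.

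**What to change.** In section 6.0 and the Arm A calendar in Appendix 5, add cholesterol and triglycerides to the day 21 blood draw already taken for the rapamycin trough in each cycle. Keep the day 1 draws, with cycle 1 as baseline, and delete *only* from footnote 8. The word in section 6.0 that limits the test to Arm A can stay.

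This schedules a value during or close to dosing in every cycle, including the last. With the window, day 21 could slip to day 24, two days after the last dose, when 0.5^(48/62) = 58% of the drug would remain; that is still well above the 15% at the nominal day 1.

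The purpose is ascertainment only, and no dose or hold rule changes. Because dosing ends on day 22, a day 21 result would do little for decisions within the same course.

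The cost is one added laboratory order per cycle on an existing draw, with no new visit or venipuncture. The reported lipid toxicity rate may rise, and on-treatment values may bring the existing 4.5.1.1 rule into play more often in the arm being tested for efficacy. The team should expect that before making the change.

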APPENDIX 5 (ARM B) Decitabine and Ribavirin

Tests	Pre										I	Days												
		1	2	3	4	5	6	7	8	9	10	11	12	13	14	15	16	17	18	19	20- 22	22-26	28	EOS
Decitabine		X	X	X	X	X	• X9	X9	X9	X ⁹	X ⁹													
Ribavirin ⁸		X ¹⁰	X 10	X ¹⁰	X	X	X	X	Х	X	X	X	X	X										
History & Physical	X	X																						
CBC w/diff & plts	X	X						X ³																
Chemistries	X	X8						X ³																
LDH	X					X		X ³																
Urate	X	X						X ⁴																
Bone marrow	X										X^1												X1	X ¹
Flow Cytometry	X																					X		
Cytogenetic Studies	X																					X		
DIC Panel	X																							
Molecular Studies ¹²	X																							
Bone marrow for Correlative Studies	X ⁵ 40cc										X ⁵ 40cc											X ⁵ 40cc		
Blood for correlative studies	X ⁷ 10cc										X ⁷ 10cc											X ⁷ 10cc		
EKG/CXR	X																							
U/A, PT, PTT, Pregnancy	X																							
Chimerism	X ²																						X ²	
Evaluation of Response																							X ⁶	X ⁶
Long Term Follow Up																								X ¹¹

 Aspirate only in cycle 1 on day 10-11 and biopsy and aspirate at days 22-26 of cycles 1 and 3 for disease assessment and at end of study. Marrows may also be performed when clinically indicated at other times for disease assessment. Substitution of peripheral blood may be acceptable if aspirate/marrow cannot be obtained.

Complion Document ID: 1248945

- 2. In those patients who have had an allogeneic transplant by chromosome (sex mismatched transplants) or by PCR assay. This can be done on either blood or marrow at physicians' choice.
- 3. Twice per week or as clinically indicated
- 4. As indicated clinically
- 5. 40 cc aspirate in green top (heparinized) tubes; if marrow is a dry tap, substitute 40 cc blood total
- 6. Cycles 1 and 3 only and at end of study or study discontinuation.
- 7. 10cc in green top tube.

- 8. After cycle 1, ribavirin will begin on day 1 and will be given continuously without interruption unless for toxicity.
- 9. Decitabine is given days 1-10 during cycle 1. In subsequent cycles, decitabine is given days 1-5.
- 10. Ribavirin is given continuously starting on day 1 of Cycle 2.
- 11. Every 6 months for up to 2 years after date of last treatment
- 12. Molecular studies completed previously are acceptable if results are in the medical record.

All time points refer to all cycles except where noted. The window for protocol visits and assessments is +/- 3 days.

